6. Research Plan:

Research Design: This is a single-blinded, randomized controlled study in which the research and care teams, including the physicians, will know which patients will receive

the integrated medical care or standard medical care.²⁸ We will execute this study under the Consolidated Standards of Reporting Trials Statement²⁸ for randomized controlled trials with the Patient Reported Outcomes extension.²⁹ There are two arms to the study, an Integrated care (ICare) arm and a Usual Care (UsCare) arm. Figure 1 (following page) provides the study flow diagram for this study. After discharge from acute care, the patient will return to the outpatient orthopaedic trauma clinic for regular follow-ups. The study team will minimize the patient burden by collecting data at the normal outpatient visits at weeks 2, 6, 12 and months six and 12. Patients will be asked for email addresses so that surveys may be emailed out, if the patient prefers. Therefore, patients may complete the surveys at home prior to their follow up visits. This will be based upon patients' preferences and resources.

Patient Sample: Patients will be recruited after admission to the University of Florida's Orthopaedic Trauma service at UF Health at Shands Hospital. The study team will determine using observation whether the patient is lucid (able to understand and recall information if medicated) at the time of approach. If not, the team will wait until the patient is able and willing to hear about this study.

Inclusion Criteria:

- Patients admitted with severe or multiple orthopedic trauma
- Aged 18-85 years
- Who have received or will receive ≥ 1 surgical procedure for their orthopedic injuries
- Any major bone fractures that impairs mobility and/or participation in activities of daily living and self-care

Exclusion Criteria:

- Aged <18 or ≥ 85 years
- Have a traumatic brain injury
- Have an inability to communicate effectively (e.g., at a level where self-report measures could be answered completely; such as medicated state or mechanically ventilated)
- Currently using psychotropic medications
- Have psychotic, suicidal or homicidal ideations.

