- **Range of Motion (ROM):** Establishing early and appropriate AROM within and at the joints above and below the injury site in the subacute/pre-structured physical therapy phase is significantly correlated⁴³ with increased functional outcomes.⁴⁴ The use of active range of motion (AROM) as a measure of functionality is common across multiple disciplines, including orthopaedics, physical therapy, and athletic training. Use of goniometer and a digital inclinometer to assess AROM have been validated.⁴⁵ For the present investigation a digital inclinometer will be utilized to measure AROM of all joints and ROMs of interest. Lower extremity range of motion will be collected for hip flexion; knee flexion/extension; and ankle plantar/dorsiflexion. Upper extremity range of motion joints will include shoulder flexion/extension, abduction, and internal/external rotation; elbow flexion/extension; wrist flexion/extension.

3. Emotional Well-Being: PROMIS™ measures of perceived well-being will include the Psychosocial Illness Impact Positive, Satisfaction with Social Roles and Activities, and Anxiety, Depression.

5. Medical Complications, Rehospitalizations and Comorbid Disease:

Electronic medical records will be used to obtain information on patients, including sociodemographic and socioeconomic characteristics, trauma injury type and severity, location and additional soft-tissue injuries. If applicable, information about the nature of the trauma will be obtained including issues that may have precipitated their orthopedic injury (e.g., drunk driving, drug use, if other individuals were injured/ killed in the accident). Additionally, Computed Tomography (CT) Scans of the thigh and abdomen, which are ordinarily obtained for orthopaedic trauma patients, will be examined to calculate visceral, intramuscular, subcutaneous adiposity, and fat free mass. Increased adiposity in these regions has been linked to decreased functional ability and recovery, as well as decreased long-term mortality.^{47,48}

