Sample Size: A sample size of 100 was determined in an *a priori* manner using G*Power software program.^{55,56} Anticipating that the study population will be younger but otherwise similarly distributed as that of Zimmerman et al.⁴² the sample size, N=100, was determined to be sufficient to have a medium effect size (Cohen's $d=0.60$, power of 0.80, and alpha of 0.05). This then translates into variable detectable mean differences depending on the outcome. For example, a 6.4 point difference in the State Trait Anxiety Index (STAI; one of the psychological measures for the study) can be detected assuming a standard deviation (SD) of 10.0; for AROM a 8.3 difference with an 12.0 SD. Linear mixed effects models will be used to analyze differences between UsCare and ICare in continuous outcomes.⁵⁷ Fixed effects will include randomized treatment group, time of measurement, baseline measurement, and covariates. An interaction term between treatment group and time will be modeled to assess how longitudinal changes in the outcomes differ between treatment groups. Subject-specific effects (random effect) will also be modelled to account for intra-individual correlation across measurement occasion. For categorical outcomes, a similar approach will be employed using generalized linear mixed models with a logit-link function (i.e. mixed-effects logistic regression). Sensitivity analyses will compare the impact of different covariance structures underlying the repeated measurements (e.g. unstructured, autoregressive,⁵⁸ and compound symmetry) on the results from the mixed-effects models.

7. Possible Discomforts and Risks:

Consent: Written informed consent will be obtained after explanation to participants about all procedures and time commitments. The team members will explain to prospective participants the purpose, methods and extent of the study. Potential participants will be asked to read the informed consent form and to ask questions.

Confidentiality: There is the potential minor risk of breach of confidentiality of information

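### The single detectable AROM difference (8.3, SD 12.0) names no joint or analysis set although any major fracture is eligible, and the functional models have no injury-region term

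*Protocol*

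**What the plan says.** **Eligibility.** The protocol's Inclusion Criteria restrict neither limb nor site: "Any major bone fractures that impairs mobility and/or participation in activities of daily living and self-care". They also admit patients with more than one orthopaedic injury.

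**What is measured.** The Range of Motion paragraph covers both limbs. For the leg, "Lower extremity range of motion will be collected for hip flexion; knee flexion/extension; and ankle plantar/dorsiflexion"; for the arm, it lists shoulder, elbow and wrist movements. The reason given for measuring AROM is early motion "within and at the joints above and below the injury site". The paragraph leaves open whether every listed joint is measured in every patient or only those near the injury. The Abstract says range of motion is first collected at the week 2 visit.

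**Sample size.** "A sample size of 100 was determined in an *a priori* manner using G*Power software program", for a "medium effect size (Cohen's $d=0.60$, power of 0.80, and alpha of 0.05"). The worked example for range of motion is "for AROM a 8.3 difference with an 12.0 SD". The documents give no expected mix of injury sites and no dropout rate.

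**Analysis.** The protocol's Statistical Analysis text and the SAP make every functional measure a dependent variable, with care approach and time point as the independent variables. The protocol's Sample Size section adds a baseline measurement and unnamed covariates. Injury region is not mentioned in either place, although the protocol has injury location extracted from the electronic medical record.

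**The concern.** A detectable difference means something only for a defined endpoint in a defined set of patients. Here one number in degrees stands for six joint regions in a population where a given joint may be near the injury in some patients and remote from it in others. There are two ways to read the measurement plan:

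- If only joints near the injury are measured, each joint has data from some unknown part of the 100.
- If every joint is measured in everyone, each joint has up to 100 patients, but some of those values come from uninjured regions, and any effect tied to the injury is averaged down.

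Under either reading, a null AROM result could be taken as evidence against a difference of 8.3 when the analysis may not have had that sensitivity. Leaving the joint and patient set open also allows them to be chosen after the data are seen.

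Injury region probably also explains much of the between-patient spread in AROM, LEGS and handgrip. For AROM, the planned baseline adjustment cannot absorb that spread, because there is no pre-treatment value.

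**Working it through.** **Inputs from the protocol's Sample Size section:** N = 100, d = 0.60, power 0.80, alpha 0.05, AROM difference 8.3, SD 12.0. **Assumed, because not stated:** two-sided test, 1:1 allocation, two-sample t-test at one time point. The numbers of patients per joint and the injured share below are also assumptions.

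**1. The plan's own figure.** With 50 per arm, the t-test detects d = 0.566 at 80% power, and 0.566 × 12 = 6.8. The stated d = 0.60 gives 0.60 × 12 = 7.2. The stated 8.3 gives 8.3/12 = 0.692. So 8.3 follows neither from d = 0.60 nor from N = 100; at N = 100 its power is 0.93. That mismatch is a separate error. Correcting it to 7.2 or 6.8 would still leave the joint and patient set undefined.

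**2. Patients needed for 8.3.** Normal approximation per arm: n = 2(1.960 + 0.842)² / 0.692² = 32.8, so 33 per arm and 66 in total. The t-test gives 33.8, so 34 per arm and 68 in total.

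**3. If only joints near the injury contribute.** Detectable difference = 12 × detectable d:

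| Patients contributing the joint (assumed) | Detectable d | Detectable AROM difference | Power for 8.3 |
|---|---|---|---|
| 100 | 0.566 | 6.8 | 0.93 |
| 68 | 0.690 | 8.3 | 0.80 |
| 50 | 0.809 | 9.7 | 0.67 |
| 30 | 1.060 | 12.7 | 0.45 |
| 20 | 1.325 | 15.9 | 0.31 |

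**4. If every joint is measured in everyone.** Suppose a true difference of 8.3 occurs only in an injured fraction f, with no effect elsewhere and SD held at 12. The average difference is 8.3 × f. With f = 0.5 it is 4.15, d = 0.346, and power at N = 100 is 0.40 (0.41 by normal approximation). For 80% power, f must be about 6.79/8.3 = 0.82.

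**5. Allowance for repeated visits.** AROM is due at five visits (weeks 2, 6 and 12, months 6 and 12). For the treatment effect averaged over five complete visits with a common correlation r, the variance is multiplied by (1 + 4r)/5. With 50 patients, r = 0.5 gives 9.70 × √0.60 = 7.5, and r = 0.7 gives 9.70 × √0.76 = 8.5. The documents give no r and no expected completeness, so these are illustrations. The calculation does not apply to the treatment-by-time interaction.

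**The case against.** The strongest objection is to a reading that a reader might easily infer: that 8.3 is out of reach for every joint. The documents do not support that. The figure needs about 68 patients, not 100. No injury mix is given that would rule out 68 for a common joint, and multiple injuries, together with counting the joints above and below each injury, raise the number per joint. The text can also be read as measuring all joints in everyone, which would put 100 patients behind each one. This part of the objection stands in full.

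The dilution figure rests on there being no arm effect in uninjured regions, which no passage states. The integrated-care arm includes a structured exercise programme and encouragement to move, neither described as limited to the injured limb. So step 4 is a scenario, not a finding. The single-visit figures also ignore the planned repeated measures; with 50 patients and r = 0.5 the stated 8.3 would be met.

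Two further inferences should be resisted. The plan nowhere proposes to pool degrees across joints. And LEGS is not shown to be uninformative after upper-limb injury: dressing, toilet transfer and reaching could plausibly be affected by it.

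AROM is a secondary measure, its figure is offered as an example, and unnamed covariates are already allowed for. These points limit the severity. They do not supply the missing joint, analysis set or region term.

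**Conclusion.** The point holds in this form: the AROM sensitivity is attached to no joint and no analysis set, in a trial open to any major fracture, and the functional models name no injury-region term.

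Its size depends on facts the documents do not give. At one time point, a joint with fewer than about 68 evenly split patients cannot detect 8.3 with 80% power. At an assumed 50, 30 or 20 patients, the detectable difference is 9.7, 12.7 or 15.9, before any gain from repeated visits. Under full measurement with the effect confined to an assumed half, power for 8.3 at N = 100 is about 0.40 instead of 0.93. It has not been shown that any particular joint falls short.

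The omission of region matters most for AROM. Collection starts at week 2, after integrated care has begun in hospital, so no pre-treatment value is available for the baseline term. Handgrip is collected in hospital and is better placed. The primary PROMIS comparisons are not touched by this point.

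**What to change.** 1. In the SAP and the protocol's statistical text, add injury region (upper, lower, both) as a pre-specified fixed effect in the mixed models for AROM, LEGS and handgrip. Code it from the injuries recorded at admission, and state beforehand how pelvic and spinal fractures are classed.
2. Restate the AROM figure as applying only to a named joint with about 68 or more contributing patients at a single time point, or remove it. If it is kept, reconcile it with d = 0.60 and N = 100.
3. State which joints are measured in which patients.
4. Keep all randomised patients as the main analysis set. Treat injured-region subsets for AROM and LEGS as supportive only, since making them primary would add many small comparisons in a trial of 100.

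**Cost:** wording in both documents and two model degrees of freedom; injury location is already extracted. The region term removes between-region variance but does not undo dilution if the effect is confined to injured regions, which is why items 2 and 3 and the supportive subsets are still needed. The restated AROM sensitivity may look less favourable.

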Randomization Process: The randomization process will be performed using a random number table and recorded separately into sealed envelopes. These envelopes will be randomly placed into patient folders. After the informed consent process, facilitator will open the randomization envelope. The patient will not know what group they have been randomized to, only the facilitator and study staff will know which group the patient is in. . .

Facilitators: The facilitators are an integral part of the study team. They have all of the proper training (IRB, HIPPA, NIH, etc.) to work with patients in health care and research settings. The Facilitators will be responsible for administering the surveys to collect the data on emotional well-being. The facilitators will also be familiarized with administering the *Transform-10* Program. The facilitators are supervised by the attending orthopaedic trauma physician ([name] or [name]), [name], and a clinical psychologist, [name]. [name], Drs. [name] and [name], and [name] will also serve as mentors for the facilitators as questions arise regarding the implementation of the *Transform-10* Program. The facilitators will make daily rounds with the trauma physician and other daily visits during the patients' hospital stay to ensure they are adhering to their treatment plan and to clarify any details about the patient's injury or treatment plan. The facilitators will serve as liaisons between the hospital staff, physician, clinic staff, and discharge planner. These individuals will be in daily communication with the study team, physician, and/or other hospital personnel to ensure patient safety and that the patients' medical questions are presented back to the attending physicians. Daily monitoring of facilitators by the attending orthopaedic trauma physician and study team will occur via morning conference prior to meeting with patients and a debriefing with the study coordinator at the conclusion of each day.

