categorical study variables and demographics (means and standard deviations for continuous variables, frequencies and percentages for categorical variables). Chi-square for frequency distributions will be used for patient satisfaction to test main effects of time and treatment and their interaction, on patient satisfaction; however, because patient satisfaction will only be measured at the end, a standard general linear model will be used. The primary analyses for all aims will utilize a mixed model repeated measures approach. These analyses can assess the main effects of treatment and time on outcomes, as well as their interaction (treatment x time). Specifically, independent variables will include care approach (integrated vs standard) and time point (admission, 2 weeks, 6 weeks, 3 weeks, month 6, and 12 months). Dependent variables will include all functional measures (actual and perceived). Mixed models are the preferred approach to analyze data with repeated measures; these models can account for correlation among repeated measurements, flexible time effects, and can handle missing data. Significant interactions between treatment and time would indicate that the change in the outcomes (i.e. slope) was dependent on the patient's treatment group. If a significant interaction is identified, the Preacher method will be used to estimate the magnitude and direction of the interaction. A p value will be established *a priori* at <0.05 for all statistical tests. Continuous data that are not normally distributed will be transformed prior to analysis. Appropriate multiple testing corrections will be performed to limit Type I error.

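### The mixed model gives the admission value one slope for all follow-up visits; adding a baseline-by-visit term would protect late comparisons at almost no cost

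*Protocol*

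**What the plan says.** The Sample Size paragraph of Protocol section 6 contains the only full model statement: "Fixed effects will include randomized treatment group, time of measurement, baseline measurement, and covariates". It continues: "An interaction term between treatment group and time will be modeled to assess how longitudinal changes in the outcomes differ between treatment groups". No baseline-by-time term is listed. A subject random effect handles the within-patient correlation, which I read as a random intercept. Unstructured, autoregressive and compound-symmetry covariances appear only as sensitivity analyses.

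The Statistical Analysis section of Protocol section 6, repeated in the SAP, describes a different model. There the independent variables are care approach and time, admission is one of the levels of time, and no baseline covariate is mentioned. The SAP does not contain the Sample Size paragraph, so it does not settle which model applies.

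On timing, the Research Design section plans "collecting data at the normal outpatient visits at weeks 2, 6, 12 and months six and 12", after an in-hospital assessment. The Study Description in the abstract says range of motion is first measured at week 2. No section gives a correlation between admission and later values, or names a primary time point.

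**The concern.** Admission values are taken in hospital shortly after acute trauma. Their link with the outcome may well be stronger at week 2 than a year later. If so, a single slope is a compromise, too shallow for the early visits and too steep for the late ones. The abstract states the investigators' belief as a long-term benefit, so the late visits matter to the trial's message.

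Two planned results could be touched. One is any treatment difference read off at a late visit. The other is the treatment-by-time test: a common baseline term cancels from within-patient changes between visits, so it explains nothing there, whereas visit-specific slopes would.

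The covariance sensitivity analyses are also harder to read. Under a common slope, changing the covariance changes the slope itself, so the month-12 estimate moves for a reason unrelated to robustness.

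**Working it through.** **The plan's own figure.** "A sample size of 100 was determined in an *a priori* manner using G*Power software program", for a "medium effect size (Cohen's $d=0.60$, power of 0.80, and alpha of 0.05". Assuming two-sided testing and 1:1 allocation (neither is stated), the normal formula gives 2(1.960+0.842)²/0.60² = 43.6, so 44 per arm. The t-test needs 45 per arm, N=90. At 50 per arm, t-test power is 0.844. So 100 is sufficient but does not reproduce exactly from the stated inputs. This does not bear on the present point; 0.844 is the unadjusted reference below.

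**Assumptions.** Equal SDs, 50 per arm, complete data, visit categorical and crossed with treatment, outcome rows from week 2. All correlations are assumed. The main case takes admission-to-visit correlations of 0.7, 0.5, 0.4, 0.3 and 0.2.

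**Formulas.** Let b be the common slope, r12 the admission-to-month-12 correlation, and the unadjusted variance be 1.
- Common slope: month-12 variance = 1 + b² − 2·b·r12. This exceeds 1 when b > 2·r12.
- Visit-specific slopes: 1 − r12².
- Random intercept: b is the mean of the five slopes. Unstructured: b = (1'S⁻¹β)/(1'S⁻¹1), where β holds the visit-specific slopes and S is the residual covariance of the follow-up visits.
- Power: noncentral t, 98 df, noncentrality 0.60·√25/√variance = 3/√variance.

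**Month 12, main case, random intercept.** b = 2.1/5 = 0.42. Variance = 1 + 0.1764 − 0.168 = 1.008. Visit-specific: 1 − 0.04 = 0.960. Ratio 1.05. Power is 0.841 with the common slope, 0.858 with visit-specific slopes and 0.844 unadjusted.

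**Month 12, main case, unstructured.** The slope now depends on the correlations among follow-up visits, also assumed. The last column is the excess variance of the week-2-to-month-12 change, worked out below.

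| Follow-up correlation | b | Month-12 variance | Excess over 0.960 | Power | Interaction excess |
|---|---|---|---|---|---|
| AR(1) by visit, 0.5 | 0.50 | 1.05 | 9% | 0.83 | 15% |
| AR(1) by visit, 0.8 | 0.57 | 1.10 | 14% | 0.81 | 27% |
| Flat, 0.4 | 0.56 | 1.09 | 13% | 0.81 | 26% |
| Flat, 0.6 | 0.67 | 1.18 | 23% | 0.78 | 45% |

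A flat follow-up correlation of 0.7, outside this range, would be worse (b=0.83, variance 1.36, power 0.72).

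**Treatment by time, week 2 to month 12.** With follow-up correlation c between these two visits, the change has variance 2 − 2c under a common slope, because the baseline term cancels. Visit-specific slopes remove a further (0.7 − 0.2)² = 0.25.
- AR(1) 0.5: c = 0.5⁴ = 0.0625, so 1.875 against 1.625 (15% more).
- Flat 0.6: 0.80 against 0.55 (45% more).

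**Milder cases.**
- Fade 0.7, 0.6, 0.5, 0.45, 0.4: b = 0.53 under random intercept, variance 0.857 against 0.840 (2%). Unstructured loses about 3-6% over the same follow-up patterns. Both remain well below 1.
- Flat 0.5: b = 0.5 and both approaches give 0.75. No loss.

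**The other reading.** If admission is an outcome row, the month-12-minus-admission contrast behaves like a change score (b = 1), with variance 2 − 2·r12. That is 1.6 at r12 = 0.2 and falls below the unadjusted 1 only when r12 exceeds 0.5.

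**The case against.** A baseline main effect is a common specification, and the case for leaving it alone has substance.

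- The larger month-12 losses come from the unstructured covariance, which the plan uses only for sensitivity. In the random-intercept model the main-case loss is 1.7 points of power, and power stays above 0.80. This stands.
- The fade has no source in the documents. Some measures may be stable: the protocol describes trait anxiety as a lasting personal feature. This stands too, so the size can be given only as a range that includes zero.
- Month 12 is not a named contrast, and the treatment main effect averaged over visits loses nothing under a random intercept, because the common slope is then the average slope. Both are correct.
- A common baseline term cancels from the treatment-by-time test, so it cannot over-adjust there. That is true, but it does not help the plan: cancelling means baseline explains none of that contrast's variance, and this is where the 15-45% arises. Week 2 to month 12 is the widest contrast; those between neighbouring visits, where the assumed slopes differ less, have less to gain.
- The Statistical Analysis section and the SAP describe a model with no common slope. This stands, and makes it necessary to say which model applies.

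A reader might infer that the common slope makes the month-12 comparison materially worse than no adjustment. For the random-intercept model the main case shows 1.008 against 1.000, and under slower or flat fades the common slope is clearly better than none. A reader might also infer bias. Randomisation keeps the treatment contrast unbiased, so the documents do not support that either.

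**Conclusion.** The point holds as a modest matter of precision. As written in the Sample Size paragraph, one baseline slope covers all follow-up visits, and the Statistical Analysis section and SAP conflict with that by making admission a level of time.

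Under an assumed fade from 0.7 to 0.2, the month-12 loss against visit-specific slopes is about 5% in variance for the random-intercept model and about 9-23% for the unstructured sensitivity model. The week-2-to-month-12 interaction contrast carries 15-45% more variance. A mild fade costs about 2-6% at month 12 and a flat correlation costs nothing. These figures rest on assumed correlations, equal SDs, complete data and 1:1 allocation.

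The point does not apply to range of motion, which has no admission value, and month 12 is not a designated primary time point. It is a cheap improvement worth making; it is not a major defect.

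**What to change.** Make the same change in the Statistical Analysis and Sample Size text of Protocol section 6 and in the SAP:

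1. State that, for outcomes measured at admission, the admission value is a covariate and the outcome rows start at week 2. Remove admission from the levels of time for those outcomes. Say separately how range of motion is modelled.
2. Add a baseline-by-visit interaction with visit categorical, alongside treatment by visit.
3. Report the visit-specific treatment differences from that model.

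With five post-admission visits this adds four slopes, so four degrees of freedom per outcome in 100 patients. It needs no new data and costs almost nothing if the correlation is flat. With complete data, and other covariates aside, the visit-specific estimates then no longer depend on the covariance structure, which makes the planned sensitivity analyses easier to interpret.

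### The primary mixed model's covariance is left to a subject random effect; if that is only an intercept and correlation fades over 12 months, some key tests exceed their nominal 5%

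*Protocol*

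**What the plan says.** The relevant text is in protocol section 6 and in the SAP.

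- **Statistical Analysis (protocol; same text in the SAP).** "The primary analyses for all aims will utilize a mixed model repeated measures approach". No random effect and no covariance structure is named. The time factor is listed as "time point (admission, 2 weeks, 6 weeks, 3 weeks, month 6, and 12 months", so admission is one of six levels of time.
- **Sample Size paragraph (protocol only).** "Fixed effects will include randomized treatment group, time of measurement, baseline measurement, and covariates", so here the admission value is a covariate. Then "An interaction term between treatment group and time will be modeled to assess how longitudinal changes in the outcomes differ between treatment groups", and for the correlation "Subject-specific effects (random effect) will also be modelled to account for intra-individual correlation across measurement occasion". Whether the random effect is an intercept alone or includes a slope is not said.
- **Same paragraph.** "Sensitivity analyses will compare the impact of different covariance structures underlying the repeated measurements", with unstructured, autoregressive and compound symmetry as examples.
- **Research Design.** The schedule is "collecting data at the normal outpatient visits at weeks 2, 6, 12 and months six and 12". I read the 3-week entry in the time list as the week-12 visit.

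Neither document names a primary covariance structure, a degrees-of-freedom method or robust standard errors, or says which result stands if the sensitivity fits disagree.

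**The concern.** A random intercept with independent residuals gives every pair of visits the same correlation and every visit the same variance. From admission to month 12 the gaps between visits are about 2, 4, 6, 14 and 26 weeks, and patients are recovering from acute injury. Scores two weeks apart will probably be more alike than scores a year apart. The model then averages high short-gap correlations with low long-gap ones, and understates the variance of contrasts that span the long gaps. The treatment-by-time tests and some 12-month comparisons would then reject too often under no effect. Sensitivity fits may show the discrepancy, but they do not alter the primary p-value. With no designated structure, the choice among fits could be made after the results are seen.

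**Working it through.** **Inputs.** N = 100 (Sample Size paragraph). The allocation ratio is not stated; I assume 1:1, so 50 per arm. Visits are at weeks 0, 2, 6, 12, 26 and 52. Tests are two-sided at 5%, data are complete and, except in step 4, variance is constant at 1. The documents give no correlations, so every correlation below is an assumption. They also give no error-rate figure for this model to reproduce. N is only an input here: a two-sample t test with d = 0.60 and 80% power needs 45 per arm, 90 in total, so 100 is not short on that calculation. That is a separate matter.

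**Step 1: 12-month difference, baseline as covariate.** Let r_j be the correlation of admission with visit j. A random-intercept fit with one baseline coefficient gives b = mean of r_j. In large samples:

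- model SE = √[(1/50 + 1/50)(1 − b²)]
- true SE = √[(1/50 + 1/50)(1 − 2b·r₅₂ + b²)]
- actual type I error = 2·[1 − Φ(1.96 × model SE / true SE)]

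Example: correlation 0.7 per visit step. The r_j are 0.700, 0.490, 0.343, 0.240 and 0.168, so b = 0.388. Model SE = √(0.04 × 0.849) = 0.184. True SE = √(0.04 × 1.020) = 0.202. The ratio is 0.912 and the error rate 7.4%.

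**Step 2: change from admission to month 12, admission as a response.** With r̄ the mean of all 15 pairwise correlations, SE ratio = √[(1 − r̄)/(1 − r₅₂)]. For the same example, √(0.524/0.832) = 0.794, giving 12.0%.

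**Step 3: simulation.** 10,000 trials per scenario with no treatment effect, fitted as a random intercept. The change column is from the step 2 formula; the others are simulated.

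| Assumed true correlation | Treatment × time, categorical (covariate / response) | 12-month difference, covariate | 12-month difference, response | Change 0-52, response |
|---|---|---|---|---|
| Constant 0.6 | 4.8% / 4.6% | 5.0% | 4.5% | 5.0% |
| 0.5 per visit step | 6.2% / 6.6% | 5.9% | 4.7% | 8.9% |
| 0.7 per visit step | 7.5% / 7.7% | 7.2% | 5.0% | 12.0% |
| Decay in weeks to 0.3 at week 52, plus 15% measurement error | 6.4% / 7.2% | 10.9% | 4.9% | 12.4% |
| Decay in weeks to 0.5 at week 52 | 8.6% / 9.3% | 18.8% | 5.3% | 17.3% |

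Step 1 agrees with the simulation: 5.8%, 7.4%, 11.9% and 19.0% for the four fading rows, against 5.9%, 7.2%, 10.9% and 18.8%. Over all fading scenarios run, the model SE was 4-33% too small for the 12-month difference with baseline as covariate, and 13-31% too small for the change contrast.

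Tests that assume no correlation pattern (Hotelling for the interaction, ANCOVA at month 12) were run in three fading scenarios. They rejected in 4.9-5.2% and 4.8-5.3%.

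**Step 4: unequal variance.** Suppose correlation is constant, admission is a response, and the SD rises in equal steps per visit from 1 to 1.25 (assumption). The mean variance is 1.273 against 1.5625 at month 12. The SE ratio is √(1.273/1.5625) = 0.903, and the 12-month test rejects in 7.7%. With a rise to 1.40, √(1.459/1.960) = 0.863, giving 9.1%.

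**Step 5: random slope added.** In separate checks under fading correlation, an intercept-plus-slope model gave about 3-6% for the 12-month difference. The interaction test still rejected in 5.2-8.6%.

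**The case against.** The strongest reply is that the plan never commits to a random intercept. The Sample Size paragraph says subject-specific effects, which may include a slope, and the Statistical Analysis text names a repeated-measures mixed model without a structure. Compound symmetry is also listed for the sensitivity comparison, which would be largely redundant if the main model already implied it. This stands: the intercept-only reading is an inference. It does not settle the matter, because error control then depends on a choice the plan does not make.

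Second, the 12-month group difference is nominal when admission is a response level, as the Statistical Analysis list has it. This stands under constant variance (4.5-5.3% in the table) but not under unequal variance (step 4). Neither document names a 12-month contrast as primary.

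Third, the planned sensitivity analyses include unstructured covariance and would expose a disagreement. This stands as partial mitigation, though no rule follows from it.

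Fourth, inflation of the categorical interaction test is modest and rests on assumed correlations. This also stands.

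A reader might also infer that the autoregressive option treats a 2-week gap like a 26-week gap. The protocol does not say whether it is indexed by visit number or by elapsed time.

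**Conclusion.** The concern holds in a conditional form. The primary covariance structure is not specified, and its simplest reading is unsafe for several contrasts the trial is likely to report. If the random effect is an intercept and correlation fades, a nominal 5% test runs at about 6-9% for the categorical interaction, 6-19% for the 12-month difference under the Sample Size paragraph's specification, and 9-17% for change from admission with admission as a response. These figures assume 50 per arm, complete data, constant variance and the correlations shown. Missing data were not simulated.

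Two stronger readings are tempting and not supported. One is that the plan fixes compound symmetry and so its 12-month intervals are always too narrow. The documents do not fix it, and under one documented handling of admission the 12-month group difference is correct if variance is constant. The other takes the protocol's gloss of the interaction as a slope to mean a linear-time test, for which a random intercept gave 12-27% in the same simulations. The plan lists discrete time points and mentions flexible time effects, so the categorical test is the fairer reading.

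**What to change.** In both documents, for continuous outcomes:

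1. Make the primary specification an unstructured covariance by visit, fitted by REML with Satterthwaite degrees of freedom.
2. Give a fixed order of fallback structures if it does not converge. A first fallback with visit-specific variances and correlation that declines with elapsed time would keep the main features; a Toeplitz structure is indexed by visit number.
3. Keep the random-effect model and the other structures as sensitivity analyses that do not replace the primary result.
4. State whether admission is a covariate or a response level, and reconcile the two passages.
5. If an autoregressive structure is kept, base it on elapsed time.

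Six occasions need 6 × 7/2 = 21 covariance parameters. Five need 15, which applies with admission as covariate and to range of motion, which starts at week 2. Either is a reasonable load for 100 patients. The cost is a few sentences in each document and a small risk of non-convergence with missing data, which the fallback order covers. If correlation and variance prove constant, little is lost.
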